12.8 ADVERSE EVENT REPORTING

This study will utilize the CTC version 4.0 for toxicity and Adverse Event Reporting. A copy of the CTC version 4.0 can be downloaded from the CTEP home page.

Toxicity Grade	Type ^a	Local IRB	Study Coordinators Via email/fax/phone
4,5	Unknown	Yes	Yes
5	Known	No	Yes*
2,3	Unknown	No	No
4	Known	No	No

^{*} If clearly related to the commercial agent(s)

12.9 ASSESSMENT OF SAFETY

12.9.1 SPECIFICATION OF SAFETY VARIABLES

Safety assessments will consist of monitoring all adverse events and reporting adverse events (AEs) and serious adverse events (SAEs) that are considered related to **Imiquimod or 9-valent HPV vaccine**, all events of death, and any study specific issue of concern.

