samples (may be drawn after randomization but must be drawn prior to treatment), endocervical specimen to be sent to Yale Pathology for high-risk HPV DNA testing (if high-risk HPV DNA results are already available, this testing may not have to be repeated) and a second endocervical cytobrush specimen for translational research purposes. Blood samples will be collected in sodium heparin tubes with about 28 cc collected each time as follows: 7 cc in each of 3 green top tubes and 7 cc in 1 EDTA/purple top tube (see follow up visits below). Endocervical specimen for high-risk HPV DNA test to be performed by Yale Pathology will be submitted in usual fashion as a SurePath specimen. Endocervical cytobrush sample for study purposes will be collected into a 50ml conical tubes containing PBS using sterile techniques and will be stored on ice until picked up by a laboratory personnel. Once all eligibility has been met the subject will be randomized to one of three arms.

Additional components of visit outline by study group:

- (1) Control group: Observation at specified study timepoints.
- (2) Imiquimod only: At the baseline visit, this group will receive instruction on imiquimod self application (16 week course) using a 6.25 mg vaginal suppository, storage of medication, possible side effects. Subjects will be provided a diary and case report form to record vaginal suppository application and side effects will be recorded per NCI Common Terminology Criteria for Adverse Events (CTCAE 4.0). Imiquimod self-application regimen will be similar to one previously described²⁴ and is as follows:
- Treatment weeks 1 and 2: Subjects apply one vaginal suppository per week
- Treatment weeks 3 and 4: Subjects apply two vaginal suppositories per week
- Treatment weeks 5 to 16: Subjects apply three vaginal suppositories per week

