Imiquimod will be dispensed in boxes containing 18 vaginal suppositories (treatment weeks 1-8) at the beginning of the treatment course. During follow up visit at week 8 (see below), subjects will be provided a new box of 24 vaginal suppositories to complete treatment course for weeks 9-16. Study drug will be prescribed by the investigator and may be dispensed either by the investigator or study staff.

6.2.2 Follow-up Visits: Follow-up visits will occur at week 8 (between weeks 7-9), at week 16 (between weeks 16-18) and once at week 22 (between weeks 20-24). For subjects randomized to treatment arms (2) Imiquimod only and (3) Imiquimod + HPV vaccine, the week 22 visit will occur at least 3 weeks after last dose of therapy. Urine pregnancy test will be performed at all follow-up visits. Subjects with exam findings concerning for worsening disease at any point in the study will be taken out of the study and treated with surgical excision procedure.

Week 8 (7-9 weeks) Visit: This visit will be timed to occur part way through the 16 week imiquimod treatment course. For women using imiquimod (Imiquimod only and Imiquimod + HPV vaccine arms), a review of medication diary, monitoring of correct use of study medication, and report of local and systemic side effects using a standardized case report form will occur at all follow up visits. For women who received HPV vaccine as part of study protocol (Imiquimod + HPV vaccine arm), a review of vaccination diary and report of local and systemic side effects using a standardized case report form will occur at all follow up visits. A pelvic exam with colposcopy will be performed to objectively assess for gross cervical lesions in all subjects and also for local side effects from imiquimod use in the Imiquimod only and Imiquimod + HPV vaccine arms. Endocervical cytobrush samples will be obtained at this time for study purposes. Cervical biopsies will be performed as clinically indicated. Blood sample collections will also occur. In addition, women in the Imiquimod + HPV vaccine groups who were previously unvaccinated will receive their booster dose of the HPV vaccine.

Week 16 (16-18 weeks) Visit: This visit will be timed to occur at completion of imiquimod treatment course. For women using imiquimod (Imiquimod only and Imiquimod + HPV vaccine

HIC#: 1603017415 Protocol version 11.0

CIN 2/3

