12.0 STUDY MONITORING AND REPORTING PROCEDURES

12.1 Personnel responsible for the safety review and its frequency:

The principal investigator will be responsible for monitoring the data, assuring protocol compliance, and conducting the safety reviews at the specified frequency which must be conducted at a minimum of every 6 months (including when re-approval of the protocol is sought). During the review process, the principal investigator will evaluate whether the study should continue unchanged, require modification/amendment, or close to enrollment. Either the principal investigator, the IRB or the Yale Cancer Center Data and Safety Monitoring Committee (DSMC) have the authority to stop or suspend the study or require modifications.

12.2 The risks associated with the current study are deemed moderate for the following reasons:

- 1. The risk of progression of CIN 2,3 to invasive cervical cancer over 6-8 months from time of initial diagnosis is low and observation of CIN 2 diagnosed in young women for up to 12 to 24 months is already recommended by the ASCCP.
- 2. The risks associated with the FDA-approved drugs imiquimod and 9-valent HPV vaccine are minimal.

Although we have assessed the proposed study as one of moderate risk, the potential exists for anticipated and/or unanticipated adverse events, serious or otherwise, to occur since it is not possible to predict with certainty the absolute risk in any given individual or in advance of first-hand experience with the proposed study methods. Therefore, we provide a plan for monitoring the data and safety of the proposed study as follows:

12.3 Attribution of Adverse Events:

Adverse events will be monitored for each subject participating in the study and attributed to the study procedures / design by the principal investigator [name], according to the following categories:

a.) Definite: Adverse event is clearly related to investigational procedures(s)/agent(s).

HIC#: 1603017415 Protocol version 11.0

CIN 2/3 26

- b.) Probable: Adverse event is likely related to investigational procedures(s)/agent(s).
- c.) Possible: Adverse event may be related to investigational procedures(s)/agent(s).
- d.) Unlikely: Adverse event is likely not to be related to the investigational procedures(s)/agent(s).
- e.) Unrelated: Adverse event is clearly not related to investigational procedures(s)/agent(s).

12.4 Plan for Grading Adverse Events:

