12.9.1.1 Adverse Events

An AE is any unfavorable and unintended sign, symptom, or disease temporally associated with the use of an investigational (medicinal) product or other protocol-imposed intervention, regardless of attribution.

This includes the following:

• AEs not previously observed in the subject that emerge during the protocol-specified AE reporting period, including signs or symptoms associated with high-grade cervical dysplasia CIN 2,3 that were not present prior to the AE reporting period. See Section 12.10.

HIC#: 1603017415 Protocol version 11.0

^a Type (Known or unknown) is based on toxicities included in the package insert or literature of known toxicities associated with the study drug(s).

CIN 2/3

28

• Complications that occur as a result of protocol-mandated interventions (e.g., cervical biopsy).

• If applicable, AEs that occur prior to assignment of study treatment associated with medication

washout, no treatment run-in, or other protocol-mandated intervention.

• Preexisting medical conditions (other than the condition being studied) judged by the investigator to have worsened in severity or frequency or changed in character during the

protocol-specified AE reporting period.

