12.9.5 Assessment of Adverse Events

All AEs and SAEs whether volunteered by the subject, discovered by study personnel during

questioning, or detected through physical examination, laboratory test, or other means will be

reported appropriately.

Each reported AE or SAE will be described by its duration (i.e., start and end dates), regulatory

seriousness criteria if applicable, suspected relationship to imiquimod or 9-valent HPV vaccine

(see following guidance), and actions taken.

To ensure consistency of AE and SAE causality assessments, investigators should apply the

following general guideline:

Yes

HIC#: 1603017415 Protocol version 11.0

CIN 2/3 29

There is a plausible temporal relationship between the onset of the AE and administration of imiquimod or 9-valent HPV vaccine and the AE cannot be readily explained by the subject's clinical state, intercurrent illness, or concomitant therapies; and/or the AE follows a known pattern of response to imiquimod or 9-valent HPV vaccine and/or the AE abates or resolves upon discontinuation of imiquimod or dose reduction and, if applicable such as in case of 9-valent HPV vaccine, reappears upon re-challenge.

No

Evidence exists that the AE has an etiology other than imiquimod or 9-vvalent HPV vaccine (e.g., preexisting medical condition, underlying disease, intercurrent illness, or concomitant medication); and/or the AE has no plausible temporal relationship to imiquimod or 9-valent HPV vaccine administration (e.g., cancer diagnosed 2 days after first dose of study drug).

Expected adverse events are those adverse events that are **listed** or characterized in the Package Insert or current Investigator Brochure.

Unexpected adverse events are those **not listed** in the Package Insert (P.I.) or current Investigator Brochure (I.B.) or not identified. This includes adverse events for which the specificity or severity is not consistent with the description in the P.I. or I.B. For example, under this definition, hepatic necrosis would be unexpected if the P.I. or I.B. only referred to elevated hepatic enzymes or hepatitis. **Refer to Section 13.0 for further guidelines**.

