15.4 Demographics, clinical measures, and safety

Summary statistics will be used to describe demographics and clinical measures collected at **baseline** using **ITT analysis set**, and will be presented by assigned treatment group and overall. Baseline characteristics will be tested for homogeneity across treatment arms using a 2-sided Fisher's Exact Test for categorical measures and ANOVA or Wicoxon Rank-Sum Test for continuous variables. Standard tables and listings will be provided for ongoing assessments, including (but not limited to) study drug dose received, treatment modifications, concomitant medications, labs, vital signs, and clinical tests, and will be reported by subject, by time point, and by treatment group, as appropriate. AEs/SAEs will be reported by subject, by time point, and by treatment group, using the **safety analysis set**.

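### Adverse events are ascertained differently in the control and active arms, and section 12.9.1 conflicts with the all-event rule in the rest of section 12

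*Combined protocol and SAP*

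**What the plan says.** **Scope of reporting.** Section 12.9.1 opens broadly: "Safety assessments will consist of monitoring all adverse events". The same sentence then narrows to "reporting adverse events (AEs) and serious adverse events (SAEs) that are considered related to" the two study products, adding all deaths and any issue of special concern. Section 12.9.1.1 defines an adverse event as one "temporally associated with the use of an investigational (medicinal) product or other protocol-imposed intervention, regardless of attribution", and lists complications of cervical biopsy as an example. Section 12.9.3 requires everything observed or reported to be collected and sent to the IRB. Section 12.9.4 requires all events in the window to be reported. Section 12.9.5 says the same of "All AEs and SAEs whether volunteered by the subject, discovered by study personnel during" questioning or found by examination or test.

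**Collection by arm.** Section 6.2.1 gives both imiquimod arms a diary and a side-effect form, and gives the vaccine arm a further form. The control entry reads "Control group: Observation at specified study timepoints". For women using imiquimod or given vaccine, section 6.2.2 adds a "report of local and systemic side effects using a standardized case report form" at each follow-up visit. The pelvic examination looks for lesions in everyone, but for local drug effects only in the active arms. The section 9.1 schedule marks a toxicity assessment before treatment and at weeks 8, 16 and 22, without limiting it by arm.

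**Analysis.** Section 15.4 states that "AEs/SAEs will be reported by subject, by time point, and by treatment group" on the safety set. Section 15.6 treats tolerability, a secondary objective (1.2.3), descriptively.

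**The concern.** Two separate problems affect the same tables.

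First, a coordinator who follows 12.9.1 and one who follows 12.9.4 would send forward different sets of events. Section 15.4 does not say whether its tables are all-cause or related-only. In an observation arm almost nothing can be judged related to a product that was not given.

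Second, even if every event counts, the arms are not asked in the same way. A diary and a structured checklist usually bring out more mild local and systemic symptoms than an open question. Vulvovaginal irritation and symptoms after biopsy can occur without any study drug. If they are solicited in two arms and left to be volunteered in the third, part of the background rate appears as a drug effect. What is at stake is the side-by-side safety description of two active treatments against observation.

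**Working it through.** The documents state no adverse event rate, so there is no figure to reproduce. The check compares the sections and then works out the direction of the bias.

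**1. Is the reporting rule consistent?** No. The second half of the 12.9.1 sentence filters on relatedness. Sections 12.9.1.1, 12.9.3, 12.9.4 and 12.9.5 do not, and nothing says which prevails.

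**2. Is collection the same in each arm?**

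| Element | Control | Imiquimod | Imiquimod + vaccine |
|---|---|---|---|
| Diary and side-effect form (6.2.1) | not specified | yes | yes, plus a vaccine form |
| Structured side-effect review at weeks 8, 16, 22 (6.2.2) | not specified | yes | yes, plus vaccine review |
| Examination for local drug effects (6.2.2) | not specified | yes | yes |
| Toxicity assessment (9.1) | yes | yes | yes |
| Open questioning (12.10.1) | yes | yes | yes |

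The last two rows are common to all arms. The first three are not.

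**3. Does the time window fit controls?** Section 12.9.4 starts the window after consent and the start of study treatment. It ends the window 30 days after the last administration or at study discontinuation or termination, whichever comes first. Controls have no start of treatment, so their window has no defined opening, and only the second closing rule could apply to them. Section 10.13 separates acute from chronic toxicity by days since treatment completion, which controls also lack.

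**4. Which way does the bias run?** Let b be the background rate of a symptom, d the true drug excess, and c the share of background events recorded in controls. Assume full capture in the active arms.

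- All-cause table: apparent difference = (b + d) − c·b = d + b(1 − c). This exceeds d whenever c is below 1.
- Related-only table: let m be the share of background events in active arms wrongly judged drug-related, with controls at zero. Apparent difference = d + m·b. This equals d if attribution is perfect (m = 0) and exceeds it otherwise.

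The following is for scale only, and all rates are assumptions. With b = 20% and d = 20 points, the all-cause difference is 20 + 20(1 − c): 20 points at c = 1, which is the truth, and 30 at c = 0.5. At c = 0.5, taking b from 10% to 30% gives 20 + 5 = 25 to 20 + 15 = 35 points. If the active arms also miss events, the overstatement shrinks, so this shows direction and not an estimate.

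**5. Attribution and grouping.** Relatedness has five levels in 12.3 and is yes/no in 12.9.5, with no mapping. The treatment-plan sections describe blinding for pathologists only (5.1, 6.2), and the arm-specific diary reviews show the arm to whoever attributes events. The safety set in 15.2 admits anyone with a relevant assessment and analyses by treatment received. It does not say where a woman assigned imiquimod who never doses would appear; one possible reading places her with controls.

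**The case against.** The strongest reply is that capture of all events in every arm is written into the protocol several times. Events are monitored for each subject (12.3). The investigator reviews all events as each subject completes (12.7). Toxicity is assessed at every study visit without restriction by arm (9.1), and elicitation should be consistent at all time points (12.10.1). Reporting in section 12 often means notifying the IRB or the monitoring committee, and 12.9.1 can be read that way. The tabulation rule in 15.4 has no relatedness filter. Tolerability is descriptive, and one of its measures, treatment interruption (10.13), cannot apply to observation.

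Much of this stands, and it rules out three stronger readings that a reader might infer.

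- *Only drug-related events are recorded.* Section 12.9.1 itself monitors all events, and the surrounding sections require them. The defect is a contradiction, not a settled related-only rule.
- *Controls will show almost no events by construction.* Controls have visits, examinations, questioning and a week 22 biopsy whose complications count. The extreme of c = 0 above (20 + 20 = 40 points) conflicts with those provisions.
- *Tolerability cannot be compared at all.* The two active arms share the imiquimod diary and form, so imiquimod effects remain comparable between them. The vaccine arm's extra form needs care for systemic symptoms.

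The reply does not give controls the structured form. Section 12.10.1 is a recommendation with sample open questions, and it does not offset diaries and checklists specified for two arms only. The window in 12.9.4 also remains undefined for controls.

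**Conclusion.** The point holds as an internal contradiction in the reporting rule together with unequal ascertainment between the active arms and control. Followed as written, the plan would produce 15.4 tables that tend to overstate the excess of events on active treatment over observation. The direction rests on two assumptions: some background symptoms occur in all arms, and structured solicitation captures more of them than open questioning. The size cannot be derived from the documents, and the figures above are illustrative. No efficacy inference is affected. Knowledge of the arm at attribution is hard to avoid against an observation control, which is a further reason not to let relatedness decide what is recorded. The placement of undosed women is an ambiguity in 15.2 and not a stated rule, and the number affected is unknown.

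**What to change.** - Reconcile 12.9.1 with 12.9.3 to 12.9.5 so that all adverse and serious adverse events are recorded in all three arms whatever their cause. If 12.9.1 is meant only for expedited notification, say so.
- Use the same symptom form and recall method in controls at weeks 8, 16 and 22 as in the active arms.
- Define the reporting window for controls, for example from randomization to the final study visit, and use the same interval in all arms for the comparative tables.
- In 15.4, tabulate all-cause and related events separately. Use one relatedness scale, or state how 12.3 maps to 12.9.5.
- In 15.2, state that any undosed women from the active arms are shown separately from controls.

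The cost is wording changes to the protocol and case report form, a few minutes per control visit, and more unrelated events in the listings. No extra visit, procedure or staff is needed, and no treatment rule changes. If some control visits have already taken place, report which visits preceded the common form, because earlier data cannot be equalised afterwards.

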12.9.1.1 Adverse Events

An AE is any unfavorable and unintended sign, symptom, or disease temporally associated with the use of an investigational (medicinal) product or other protocol-imposed intervention, regardless of attribution.

This includes the following:

• AEs not previously observed in the subject that emerge during the protocol-specified AE reporting period, including signs or symptoms associated with high-grade cervical dysplasia CIN 2,3 that were not present prior to the AE reporting period. See Section 12.10.

HIC#: 1603017415 Protocol version 11.0

^a Type (Known or unknown) is based on toxicities included in the package insert or literature of known toxicities associated with the study drug(s).

CIN 2/3

28

• Complications that occur as a result of protocol-mandated interventions (e.g., cervical biopsy).

• If applicable, AEs that occur prior to assignment of study treatment associated with medication

washout, no treatment run-in, or other protocol-mandated intervention.

• Preexisting medical conditions (other than the condition being studied) judged by the investigator to have worsened in severity or frequency or changed in character during the

protocol-specified AE reporting period.

12.9.2 Serious Adverse Events

Refer to Section 13.0 of the study protocol.

12.9.3 Methods and Timing for Assessing and Recording Safety Variables

The investigator is responsible for ensuring that all AEs and SAEs that are observed or reported

during the study, as outlined in Section 12.10 and 13.0 respectively, are collected and reported to

the appropriate IRB(s).

12.9.4 Adverse Event Reporting Period

The study period during which all AEs and SAEs must be reported begins after informed consent

is obtained and initiation of study treatment and ends 30 days following the last administration of

study treatment or study discontinuation/termination, whichever is earlier. After this period,

investigators should only report SAEs that are attributed to prior study treatment.

